### **Secondary Endpoints**

The secondary endpoints are how many additional lesions were needed to terminate VT, if any, and procedure duration.

- a. We anticipate that 10 participants will be adequate to describe the association of the virtual heat guided ablation lesions and acute VT non inducibility.
- b. Early stopping rules. We anticipate no untoward effects from this research. However, if any adverse events are noted the study will be terminated.

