### 1. Abstract

Ventricular tachycardia (VT), a life-threatening fast heart rhythm, occurs frequently in patients with myocardial infarction, leading to sudden cardiac death. Catheter-based ablation, the delivery of energy to destroy the ability of cardiac tissue to conduct electrical signals, offers the possibility of permanent cure by interrupting the VT reentrant circuit. Unfortunately, eliminating infarct-related VT with ablation has achieved only modest success, 50-88%, and with complication rates as high as 8% of the treated population. This stems from limitations in current electrical mapping techniques used to identify the target locations for ablation. These include limited sampling during mapping, with resolution often insufficient to identify critical arrhythmia circuits, the hemodynamic intolerance during VT induction, and the ambiguities in correlating electrical maps with heart anatomy. Furthermore, the complex three-dimensional pathways of cardiac impulse propagation around/through the zone of infarct during VT are difficult to reconstruct by mapping the ventricular surfaces only. These limitations translate into inaccurate ablation targets and extensive unnecessary lesions, and into prolonged duration of the procedure, dramatically increasing the risk of chamber injury, thromboemboli, bleeding, and radiation overexposure. Our Hopkins team has developed a novel “virtual-heart” methodology that could eliminate the need for invasive electrical mapping in determining the optimal targets for infarct-related VT ablation. The approach is based on cardiac imaging and computational modeling, and is personalized to each patient. The methodology involves constructing three-dimensional computer models from patients’ CMR data. We then execute simulations with each virtual heart to evaluate all possible patient-specific VTs, and to determine automatically, using a novel algorithm, the optimal ablation targets that render, with minimum lesion size, each heart not inducible for VT.. The approach thus targets termination not only of VTs that are clinically manifested or induced at the time of procedure, but of all VTs that could arise from the given post-infarction substrate, including those that might arise following initial ablation, thus potentially eliminating the need for repeated ablations and offering long-term freedom from VT.

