**4. Study Procedures**

a. Study design, including the sequence and timing of study procedures (distinguish research procedures from those that are part of routine care).

1. Potential participants will be obtained from the Johns Hopkins Hospital electrophysiology lab inpatient and outpatient schedule and from the Johns Hopkins outpatient cardiac electrophysiology clinic, who have a planned procedure for catheter ablation of ventricular tachycardia.
2. Participants will undergo written consent.
3. The participant will then undergo a cardiac MRI scan performed with a 1.5-T MRI scanner, with delayed late gadolinium enhancement. Cardiac MRIs or CTs are part of the routine care at Johns Hopkins among patients presenting for a ventricular tachycardia catheter ablation.
4. MRIs should be acquired no more than 30 days and no fewer than 24 hours prior to a scheduled ablation procedure. If the patient has prior MRI data available matching the specified image parameters, from fewer than 30 days prior to the procedure, those data may be used instead.
5. The cardiac MRI will then be processed and simulations performed with each virtual heart to evaluate all possible patient-specific VTs, and to determine the optimal ablation targets.
6. In the event that a patient is enrolled, but a satisfactory, good quality MRI cannot be obtained, the patient will remain enrolled, but the guided ablation procedure will not be performed and the patient will undergo a standard ablation procedure. Other than this

notation of data, the procedure will be the same as if the subject were not enrolled in the study.

7. If a good quality cardiac MRI is obtained and a virtual heart model with the ablation targets is generated, the operating physician will merge the virtual heart lesion map to the invasive electroanatomical navigation system. After the patient has been catheterized, an attempt should be made to induce VT. The physician should then navigate the catheter to each of the ablation targets specified, and place a lesion as per his or her training and experience, confirming when done that the lesion marker in the mapping system coincides with the target. This will be done for each lesion.

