## **8. Risks**

### **Ablation Risks**

Standard ablation procedures include all of the operations that will be performed as part of the study, including induction of VT and termination of VT, pace mapping, and creation of lesions via radiofrequency energy. The study requires one additional attempt to induce VT, out of multiple attempts typically done during such a procedure. The study requires that the ablating physician ablate the predicted lesion sites first. If the hypothesis of this trial is correct, the number of lesions delivered will be smaller than usual. It is possible that several lesions might be added to the total number normally done during such a procedure. However, frequently multiple lesions are placed during such a procedure.

The acute harm associated with induction of ventricular tachycardia is patient hemodynamic instability. The acute harm associated with ablation lesions are in line with the risk of the procedure which includes pain, damage to heart valve, lung or heart perforation which could require emergency intervention or surgery, heart block, stroke or TIA, pulmonary embolism, myocardial infarction, phrenic nerve paralysis and death.

There is no clear long term harm from induction of ventricular tachycardia during an electrophysiology procedure. The long term harm associated with unnecessary ablation lesions in areas of diseased myocardial tissue is not clear.

In order to minimize risk, all procedures will be performed with cardiac anesthesiology support. Throughout the procedure, continuous hemodynamic monitoring including non-invasive/invasive measurements of blood pressure, heart rate, oxygen saturation and respiratory status will be performed. Ablation will only be performed by an experienced operator, using tools approved for the indication on diseased tissue which is important in the substrate for ventricular tachycardia.

All adverse events related to an electrophysiology procedure at the Johns Hopkins Hospital is recorded in a HIPAA secure RedCap database. Adverse events are assessed at the time of the procedure and at each subsequent clinic visit. Any unanticipated problems involving risk to subjects or others will be reported to FDA within 10 working days after receiving notice of the adverse effect.

Major complications are defined as life-threatening, leading to permanent harm, or necessitating intervention or prolonged hospitalization within 30 days of ablation.

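### The stopping rule in section 7, item b ends the study on any adverse event, so read literally a minor, expected event of a required step can end it

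*Protocol*

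**What the plan says.** The early stopping rule is in Protocol section 7, item b, printed under Secondary Endpoints. It opens with "We anticipate no untoward effects from this research" and then, after a "however", states that "if any adverse events are noted the study will be terminated". It gives no seriousness grade, exclusion of expected events, event count or review step.

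Section 8 (Ablation Risks) describes what the study adds to routine care: "The study requires one additional attempt to induce VT, out of multiple attempts typically done during such a procedure", and "The study requires that the ablating physician ablate the predicted lesion sites first". It names hemodynamic instability as the acute harm of inducing VT. The harms it lists for lesions run from pain to perforation, stroke and death. The abstract lists "the hemodynamic intolerance during VT induction" among the limits of current mapping and describes conventional ablation as carried out "with complication rates as high as 8% of the treated population".

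Section 8 also defines major complications (30-day window) and refers to unanticipated problems. Item b uses neither term. Section 4.b gives the planned size as 10 participants.

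**The concern.** The rule is mandatory and its trigger has no lower bound. The steps the study requires have known acute harms, some of them minor, and section 8 has adverse events assessed at the procedure and at each later clinic visit, so such events can be noted.

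Two things are at stake. If the rule is followed to the letter, an expected event such as pain or transient instability closes a very small series without any information on whether the predicted targets work or are safe. If it is not followed to the letter, someone decides after the event which events count, with no written criterion. That weakens the protection the rule is meant to give.

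This is not detail left to an analysis plan. The protocol states a rule, and the rule is badly fixed.

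**Working it through.** **Step 1: the wording.** The only candidate limit is the reference to the research in the sentence before the rule.

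- *If only effects of the research count:* the added induction and the first-placed target lesions are research steps. Section 8 names instability and pain as harms of induction and of lesions. A minor, expected effect of either step still meets the trigger.
- *If every event counts:* background complications of the routine procedure meet it as well.

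On both readings an expected event can end the study, because neither supplies a limit by seriousness or expectedness.

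**Step 2: the size for complications alone.** The protocol gives no stopping probability, so there is no figure to reproduce.

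Inputs:
- n = 10 (section 4.b).
- p = chance of a counted event per patient. The 8% is the abstract's upper figure for complications of conventional ablation; 2% and 5% are assumed.
- Patients are independent, and each event is noted before the next patient is treated (assumed).

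Stop before the tenth patient: 1 − (1 − p)^9. Expected patients lost from the series: 10 − [1 − (1 − p)^10]/p.

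| p | Stop before patient 10 | Expected loss of 10 |
|---|---|---|
| 2% (assumed) | 1 − 0.98^9 = 16.6% | 10 − 9.15 = 0.85 |
| 5% (assumed) | 1 − 0.95^9 = 37.0% | 10 − 8.03 = 1.97 |
| 8% (protocol ceiling) | 1 − 0.92^9 = 52.8% | 10 − 7.07 = 2.93 |

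The chance passes one half only when p exceeds 1 − 0.5^(1/9) = 7.4%, just below the ceiling.

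**Step 3: minor events.** The protocol gives no rate for these. Purely as illustration, if the chance of any counted event were 10%, 20% or 30% per patient, the same formula gives 61%, 87% and 96%.

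**Step 4: the replacement rule.** Let f be the fraction of complications judged related or possibly related. Suppose all 10 patients are guided and every complication is major. Termination before the tenth patient then has probability 1 − (1 − f·p)^9. At p = 8%:

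- f = 0: 0%
- f = 0.5: 1 − 0.96^9 = 30.8%
- f = 1: 1 − 0.92^9 = 52.8%, the same as under the current rule

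Pauses are not counted here. The values of f are assumptions.

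**The case against.** The strongest defence reads the two sentences of item b together. Section 8 openly anticipates instability, pain and worse, and says standard ablation contains every operation used in the study, "including induction of VT and termination of VT, pace mapping, and creation of lesions via radiofrequency energy". To agree with that, the untoward effects in item b would have to mean harm beyond the routine procedure, and expected harms would not stop the study. This reading is possible and may be what was intended. It is not in the text, however, and a mandatory stopping rule should not depend on inference.

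It can also be said that instability during an intended, monitored induction is hardly an adverse event, and that the abstract's remark on intolerance concerns mapping in general. Both are fair and weaken any attempt to put a number on minor events. They do not supply the missing limit.

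A first-event stop can be a sound, cautious choice in 10 patients, and stopping early harms none of them. That stands as an argument for keeping a strict rule. A strict rule still needs a defined event.

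Three stronger inferences are tempting and not supported:

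- *That the study is almost certain to stop.* The 61% to 96% rest on assumed rates only.
- *That the sponsor means to count events in patients who get no guided ablation.* Section 4.a, item 6 says that without a good MRI "the patient will remain enrolled, but the guided ablation procedure will not be performed and the patient will undergo a standard ablation procedure", so the literal wording reaches them. That is an ambiguity, not a stated intent.
- *That an early stop would invalidate the result.* The primary endpoint is acute, and each treated patient's outcome is already complete.

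**Conclusion.** The point holds and should be fixed; its weight is minor to moderate. As worded, item b lets a minor, expected event of a required step end the study, and nothing else in the protocol narrows it. This conclusion rests on the text and needs no event rate.

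The size is less firm. The 53% takes the protocol's upper figure for conventional ablation as the per-patient complication rate and assumes independent patients and immediate detection. At an assumed 2% the chance is 17% and the expected loss is under one patient. Minor events would push the chance up by an amount the protocol does not allow one to state. The cost is a shorter descriptive series and a stop that may say nothing about the targets.

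**What to change.** Reword section 7, item b along these lines:

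> The study is terminated if a major complication (as defined in section 8) or an unanticipated problem is judged related or possibly related to the virtual-heart-guided lesions or the added VT induction. Any other major complication in a guided patient, and any other non-major adverse event judged related to the guided lesions beyond expected procedural pain or transient instability during induced VT, pauses enrolment for investigator review. Termination of an induced VT by pacing or cardioversion is part of the procedure. All other adverse events are recorded and reported but do not stop the study.

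The pacing and cardioversion sentence is needed because the section 8 definition takes in events that need an intervention, while the same section treats ending VT as a standard step. The pause for related non-major events matters because some listed harms, for example a TIA that resolves without intervention or a longer stay, would otherwise be recorded only.

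Gain: expected minor events and clearly unrelated complications no longer end the study. At equal n there is no gain on complications if every one is judged possibly related: 53% under either rule at 8% and n = 10.

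Cost: a wording amendment with IRB approval; no added patients, visits or procedures. Section 8, item a already sends unanticipated problems to the study investigators, who can do the review. The stop becomes less strict: unrelated major complications and related non-major events lead to a pause, and expected minor events to recording only.

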## **8. Risks**

### **Ablation Risks**

Standard ablation procedures include all of the operations that will be performed as part of the study, including induction of VT and termination of VT, pace mapping, and creation of lesions via radiofrequency energy. The study requires one additional attempt to induce VT, out of multiple attempts typically done during such a procedure. The study requires that the ablating physician ablate the predicted lesion sites first. If the hypothesis of this trial is correct, the number of lesions delivered will be smaller than usual. It is possible that several lesions might be added to the total number normally done during such a procedure. However, frequently multiple lesions are placed during such a procedure.

The acute harm associated with induction of ventricular tachycardia is patient hemodynamic instability. The acute harm associated with ablation lesions are in line with the risk of the procedure which includes pain, damage to heart valve, lung or heart perforation which could require emergency intervention or surgery, heart block, stroke or TIA, pulmonary embolism, myocardial infarction, phrenic nerve paralysis and death.

There is no clear long term harm from induction of ventricular tachycardia during an electrophysiology procedure. The long term harm associated with unnecessary ablation lesions in areas of diseased myocardial tissue is not clear.

In order to minimize risk, all procedures will be performed with cardiac anesthesiology support. Throughout the procedure, continuous hemodynamic monitoring including non-invasive/invasive measurements of blood pressure, heart rate, oxygen saturation and respiratory status will be performed. Ablation will only be performed by an experienced operator, using tools approved for the indication on diseased tissue which is important in the substrate for ventricular tachycardia.

All adverse events related to an electrophysiology procedure at the Johns Hopkins Hospital is recorded in a HIPAA secure RedCap database. Adverse events are assessed at the time of the procedure and at each subsequent clinic visit. Any unanticipated problems involving risk to subjects or others will be reported to FDA within 10 working days after receiving notice of the adverse effect.

Major complications are defined as life-threatening, leading to permanent harm, or necessitating intervention or prolonged hospitalization within 30 days of ablation.

a. Plan for reporting unanticipated problems or study deviations.

Unanticipated problems will be reported to the study investigators along with the referring physician. Study deviations will be communicated with the study participant.

b. Legal risks such as the risks that would be associated with breach of confidentiality.

Not applicable.

c. Financial risks to the participants.

There are no financial risks to the participant.

## **9. Benefits**

There are no direct benefits from participation in this study. The benefit of this study is to better understand the mechanism and optimal ablation sites for those presenting to the electrophysiology lab for the catheter ablation of VT. The goal is using our protocol will lead to decreased procedural times, decrease patient risk and improved efficacy for the catheter ablation management of VT.

## **10. Payment and Remuneration**

Monetary compensation will not be provided to the participants.

## **11. Costs**

There will be no cost for the participant in this study.
